The BENDITA trial was a randomized, double-blind, phase II, placebo-controlled trial conducted in Bolivia between 2016 and 2018. (27) Two-hundred and ten participants at chronic phase CD were randomized in seven groups, each group receiving BZN in shorter regimens and in combination with fosravuconazole: BZN 300 mg daily for 8 weeks, 4 weeks, or 2 weeks, BZN 150 mg daily for 4 weeks, BZN 150 mg daily for 4 weeks plus fosravuconazole, BZN 300 mg once per week for 8 weeks plus fosravuconazole, or placebo, with 30 participants in each group and a 12-month follow-up period. The intention-to-treat primary efficacy analysis showed that 89.3% had sustained clearance at 6 months on parasitemia on BZN 300mg 8 weeks and 4 weeks; 82.8% on BZN 300mg 2 weeks; 83.3% on BZN 150mg 4 weeks; 85.2% on BZN 150mg 4 weeks in combination with fosravuconazole and 82.8% on BZN 300mg weekly in combination with fosravuconazole, compared with 3.3% for placebo. Safety results suggested high adherence to treatment in all groups. Six participants (20%) discontinued treatment of BZN 300mg 8 weeks; 1 (3.3%) in 4 weeks; none in 2 weeks; 1 (3.3%) in BZN 150mg 4 weeks; 3 (10%) in BZN 150mg 4 weeks in combination with fosravuconazole and 4 (13.3%) in BZN 300mg weekly in combination with fosravuconazole. Most adverse events (AE) were mild to moderate, with only 6 participants presenting with serious adverse events (SAE). No SAEs were reported in BZN 300mg 2 weeks and 150mg 4 weeks. There are no differences between 4 weeks and 2 weeks arms regarding parasitological response or safety.

These results suggest that a shorter treatment with BZN effectively sustained parasitological clearance, was well tolerated, and has the potential to be a new therapeutic regimen for participants with chronic CD. Therefore, the current study proposes to evaluate a shortened therapeutic regimen with a larger number of participants.

Recently, the MULTIBENZ clinical trial, a phase IIb non-inferiority, randomized, blind, multicenter and international clinical trial, designed to evaluate the efficacy and safety of three different BZN regimens for the treatment of chronic phase CD, was completed. The study was conducted in four different countries: Argentina, Brazil, Colombia and Spain. (33)

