5.1 Eligibility criteria

5.1.1 Inclusion Criteria

- Adults aged ≥ 18 years;¹
- CD diagnosis through the positivity of two serological tests that use different antigens (recombinant and native antigens, according to World Health Organization (WHO) recommendations) (28).
- Informed consent form read and signed by the participant.
- Weight ≥ 50 kg to ≤ 95 kg.
- Ability to carry out all tests and visits to the protocol site and have a fixed address.
- Women of childbearing age should have a negative urine or serum pregnancy test at baseline.

¹ It is considered that neither the dynamics of parasitemia, nor the therapeutic response and safety profile, demonstrate differences in the chronic phase adult population up to 60 years of age. Considering that there is no contraindication for administering antiparasitic treatment beyond 60 years of age, and that the objective is to see the antiparasitic effect and the safety profile, recruiting patients older than 60, which will allow a greater probability of recruiting patients in the shortest possible time, optimizing studytimes, financial resources, and the opportunity to have the results available.

A contraceptive method should be used.²

Note that although PCR will be determined at baseline, this will not be considered as an inclusion criterion.

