6.9.3 Neutropenia

Hematological assessments will be performed as previously described. If Absolute Neutrophil Counts \leq 1000 cells/ μ l are documented, treatment should be discontinued, and CBC will be repeated as soon as possible after the initial abnormality is identified. After that, the participant should be followed every 48 hours (2 days), or the closest possible interval, until the neutrophil counts increase above 1000 cells/mm or stabilize. The event should be immediately reported as an SAE.

In case Absolute Neutrophil Count is found to be $<$ 500 cells/ μ l, the treatment should be immediately interrupted, and a control hematological assessment is required within one day. Participants will be instructed to avoid exposure to people with respiratory tract infections and to respect general hygiene rules. Depending on profile (decreasing phase, stabilization phase, resolution phase), controls will be required every one to three days until normalization. The event should be immediately reported as an SAE.

In case Absolute Neutrophil Count is found to be $<$ 100 cells/ μ l, or below 1000 with associated fever (even of mild intensity) or infectious origin symptoms, the participant should immediately be hospitalized and reported as an SAE.

7. Laboratory assessment

Blood samples for hemogram and biochemistry (5mL each) will be collected in the same day at screening, at days 14 (allowable window of + 2 days), and 56 (allowable window of + 7 days).

Blood samples for serology will be collected at screening visit and at month 24 after EOT.

Blood samples for PCR will be collected at screening visit and at 1, 4, 6, 8, 12, 18 and 24 months after EOT (allowable window of + 10 days. Blood samples collected for PCR shall be immediately added to a tube containing one volume (5mL) of a solution of Guanidine/ClH 6M EDTA 0.2M pH 8,0 Buffer (GEB). Samples

with guanidine buffer can remain at room temperature. Trained nurses will be responsible for the blood collection, sample processing and storage.

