10.1 Sample Size Determination

A total sample size of 672 subjects (224 per trial arm, and 336 per country) will be necessary to achieve 90% power to detect a non-inferiority margin difference of 15%, assuming that the standard regimen failure rate is 10% and the intervention regimen is 12%, for a one-sided Z test at a significance level of 0.025. This total sample size has been increased in anticipation in 40% to assure a minimum 60% of participants with active infection (positive PCR) and further by 10% to account for potential losses to follow-up, in order to maintain the specified power and inferiority/superiority margins. This means that individuals removed from the study for the reasons mentioned will not be replaced. This sample size will allow the study to also demonstrate a superiority margin of difference of 10% with 80% power regarding the safety of the experimental arm. Considering the percentage of treatment interruption for conventional treatment of 20%, and a reduction of 50% in the experimental arm, power of 90% and $\alpha=0.05$, 197 patients will be needed in each arm.

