10.2 Populations for Analyses

For analysis purposes, the following populations are defined and will be described in greater detail in the trial Statistical Analysis Plan:

Population	Description
Intention to Treat (ITT)	All enrolled participants who are randomized into the study.
Per Protocol	All patients completing the study without major protocol deviations. Patients with a positive PCR result prior to time of exclusion, will be included and considered as treatment failure.
Safety population	All subjects who received at least one dose of study medication.

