10.3 Statistical Analyses

Categorical variables will be presented as frequencies and percentages and continuous variables as median (interquartile range) or mean (standard deviation) according to the data distribution. Normality of distribution will be checked through histograms and the Kolmogorov-Smirnov test.

The chi-squared test or Fisher exact test will be performed to compare the frequencies across categorical variables and the Mann-Whitney test or Student t-test will be used to compare the continuous variables. Intention-to-treat analysis will be performed to evaluate the efficacy and safety that includes all participants randomized to the study groups. The primary analysis will compare proportion of patients with sustained negative PCR at 24 months in their randomly assigned treatment groups (intention-to-treat analysis). Moreover, the proportion of participants with adverse drug events will be also compared. Comparison analyses between groups will be performed using generalized linear models with a log-link

and binomial distribution. Longitudinal differences on quality-of-life scores between groups will be fitted using linear mixed models.

A per protocol analysis will also be performed. Those participants who do not comply with treatment or permanently interrupt or modify the proposed treatment will be excluded from the analysis unless they had a positive PCR prior to that time-point, in which case they will be included in the analysis and considered as a treatment failure.

For PCR analyses, means and bilateral 95% confidence intervals will be presented by group and visit. In addition, time to sustained parasite clearance until 6, 12, 18 and 24 months of follow-up visits will be assessed using Kaplan–Meier survival analysis with log rank test for significance. Repeated measures analysis will also be performed.

Statistical significance will be set at 0.025 for the non-inferiority outcome (positive PCR) and 0.05 for the superiority outcome (percentage of adverse drug reactions and QOL).

The interim analysis for early stopping will be based on superiority and conducted when all participants have reached 12 months of follow up since the end of treatment. An independent data and safety monitoring board (DSMB) will be convened for this study with expertise in CD, clinical trials as well as biostatistics. The purpose of the DSMB is to analyze the preliminary data at 12 months to help in the decision of interrupting any arm.

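### As written, the per-protocol rule can count a pre-treatment PCR as treatment failure, which tilts the secondary per-protocol comparison towards non-inferiority

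*Protocol*

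**What the plan says.** Section 10.3 makes intention-to-treat the primary analysis and adds a per-protocol analysis. From the latter, participants who do not comply with, permanently interrupt or modify treatment are "excluded from the analysis unless they had a positive PCR prior to that time-point, in which case they will be included in the analysis", as treatment failures. The per-protocol entry in section 10.2 reads: "Patients with a positive PCR result prior to time of exclusion, will be included and considered as treatment failure". Neither sentence limits the PCR to samples taken after treatment.

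On timing, section 7 states: "Blood samples for PCR will be collected at screening visit and at 1, 4, 6, 8, 12, 18 and 24 months after EOT". The schedule of activities (section 12) agrees: no PCR at day 0, 14, 28 or 56. On entry, section 5.1.1 notes that "although PCR will be determined at baseline, this will not be considered as an inclusion criterion", so participants positive and negative at screening are both enrolled.

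Two other places bear on the rule. The interim-analysis text of section 10.3 takes failure to be one or more positive PCRs during follow-up. Section 9.12 keeps participants who stop treatment in the planned visits, so their post-treatment PCR results should exist.

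**The concern.** Non-compliance and interruption happen within the 8 weeks of dosing, when no PCR is taken. A rule that looks back from that moment for a positive PCR can find only the screening sample. Followed to the letter, it labels a participant a treatment failure on a sample drawn before the first dose, and overrides the follow-up results that the trial will have.

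The error does not fall evenly. The protocol expects more interruption on 8 weeks than on the shorter courses, so in each pairwise comparison more automatic failures land in control than in the short arm. That raises the control failure rate more and narrows, or reverses, the difference being tested. In a non-inferiority trial the per-protocol set is useful because it can show a loss of efficacy that non-adherence blurs under intention-to-treat. A rule that works the other way removes that check.

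**Working it through.** **Inputs.**
- Failure 10% control, 12% short arm; margin 15 points; one-sided 0.025; power 90%; 224 per arm; 10% losses (section 10.1).
- Baseline PCR-positive share b = 0.60, the minimum in section 10.1.
- Interruption d: "percentage of treatment interruption for conventional treatment of 20%, and a reduction of 50% in the experimental arm" (section 10.1), so 0.20 and 0.10.
- Phase II discontinuation: "Six participants (20%) discontinued treatment of BZN 300mg 8 weeks; 1 (3.3%) in 4 weeks; none in 2 weeks" (section 2.2), about 30 per group.

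**The plan's own figure.** n = (1.96 + 1.2816)² × (0.10 × 0.90 + 0.12 × 0.88) / (0.15 − 0.02)² = 121.6, so 122 per arm. Then 122 / 0.6 × 1.1 = 223.7, so 224. This matches the stated sample size and confirms 60% as the working baseline share.

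**Literal rule.** With f the failure rate among those who complete treatment, a share (1 − d) stays in with failure rate f, a share d × b stays in as certain failures, and a share d × (1 − b) is dropped:

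per-protocol failure = [(1 − d)f + d·b] / [(1 − d) + d·b]

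- Control: (0.8 × 0.10 + 0.2 × 0.6) / (0.8 + 0.12) = 0.200 / 0.92 = 21.7%.
- Short arm, f = 0.12: (0.9 × 0.12 + 0.1 × 0.6) / (0.9 + 0.06) = 0.168 / 0.96 = 17.5%.
- Difference: −4.2 points instead of +2.0, a shift of 6.2 points.
- Automatic failures out of 224: 224 × 0.2 × 0.6 = 26.9 in control, 224 × 0.1 × 0.6 = 13.4 in each short arm.

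**At a true 15-point deficit (10% versus 25%).** Short arm: (0.9 × 0.25 + 0.06) / 0.96 = 29.7%. The apparent difference is 29.7 − 21.7 = about 8 points. With 224 × 0.9 = 202 followed per arm, the set keeps 202 × 0.92 = 185.8 control and 202 × 0.96 = 193.9 short-arm participants; the unpooled SE is 0.0446.

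P(non-inferiority) = Φ((0.15 − 0.0795) / 0.0446 − 1.96) = Φ(−0.38) = 35%, against 2.5% if all interrupters are excluded.

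**Range at that deficit, literal rule.**

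| Interruption, control / short | Baseline positive | 202 per arm | 224 per arm |
|---|---|---|---|
| 20% / 10% | 60% | 35% | 38% |
| 20% / 10% | 80% (assumed) | 50% | 54% |
| 20% / 10% | 100% (assumed) | 63% | 68% |
| 20% / 3.3% (phase II, 4 weeks) | 60% | 65% | 70% |
| 20% / 0% (phase II, 2 weeks) | 60% | 78% | 82% |
| 10% / 10% (assumed) | 60% | 4.1% | 4.2% |
| 20% / 20% (assumed) | 60% | 6.2% | 6.5% |

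**Reading 2: only follow-up PCR counts.** Nobody who stops during treatment has a prior follow-up PCR. The exception is empty for them, they are all excluded, and the rates stay at 10% and 12%.

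**Reading 3: the time of exclusion in section 10.2 is a later date.** Interrupters then enter only if they fail. With g their failure rate, the per-protocol rate is [(1 − d)f + d·g] / [(1 − d) + d·g].
- g = 10% / 12%: control 0.10 / 0.82 = 12.2%, short arm 0.12 / 0.912 = 13.2%; difference +1.0 instead of +2.0.
- g = 40% in both (assumed, not in the protocol): 0.16 / 0.88 = 18.2% and 0.148 / 0.94 = 15.7%; difference −2.4.

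Section 10.8 counts end of treatment from each arm's own dosing duration, which would put a 1-month sample for the 2-week arm at about week 6. The schedule has no PCR there, so the timing argument stands.

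**The case against.** The best defence is that nobody means a screening sample to count. Section 10.3 ties failure to follow-up PCR, section 10.8 defines the endpoint as sustained clearance after treatment, and most participants are expected to be positive at entry. Section 10.2 leaves detail to the statistical analysis plan, which is not available here and could say which samples count. Keeping someone who was PCR-positive at month 6 and left at month 12 as a failure is also sensible.

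Much of this stands. The literal reading may not be intended, and under the follow-up definition the clause does nothing for those who stop during treatment. A reader might infer that per-protocol membership depends on the outcome under every reading; it does not under that one. What the defence does not remove is that both sentences state an operative rule without the limit, that section 10.3 ties it to treatment interruption, and that followed literally it conflicts with the failure definition in the same section. That is more than detail left for later.

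Three stronger inferences should also be resisted:
- The 35% and 78% are not the trial's risk of a false claim. They belong to the per-protocol analysis alone; the protocol nowhere makes a non-inferiority claim conditional on it.
- The excess in control is per comparison. On the planning rates the two short arms together receive as many automatic failures (2 × 13.4) as control (26.9).
- Not every retained interrupter is a false failure. Some would fail anyway; the rule ignores which.

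**Conclusion.** The point holds as a fault in the wording of a secondary analysis set. Followed as written, the rule counts a pre-treatment PCR as failure, contradicts the protocol's failure definition, and moves the planned per-protocol difference from +2.0 to −4.2 points. At a true 15-point deficit that analysis would show non-inferiority in about 35% of trials with 202 per arm. The 78% figure needs zero interruption in the short arm, an extrapolation from about 30 phase II participants, and should be read as an upper scenario at 60% baseline positivity.

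These sizes assume the literal reading, that the 20% and 10% are permanent stops during treatment, independence of interruption and baseline PCR, and completers failing at the planned rates. If only follow-up PCR counts, no failures are added. If exclusion means a later date, a modest tilt towards non-inferiority remains, about 1 point when interrupters fail at 10% and 12%. The primary intention-to-treat result is unaffected under any reading.

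**What to change.** In sections 10.2 and 10.3:
- Define per-protocol membership from treatment exposure and major deviations, decided blind to PCR, so that those who stop or do not comply during treatment are excluded whatever their PCR.
- Keep the positive-PCR exception only for a positive follow-up PCR (month 1 after end of treatment or later) obtained before a post-treatment deviation or study withdrawal.
- State that the screening PCR never counts as treatment failure.

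The cost is two sentences and a slightly smaller per-protocol set: with 202 followed per arm and the planning rates, about 24 fewer in control (202 × 0.2 × 0.6) and 12 fewer in a short arm (202 × 0.1 × 0.6) than under the literal rule. At 10% versus 12% failure, the chance of showing non-inferiority in the reduced set is still about 97%.

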3.1 Assessment of Efficacy

Efficacy of study treatment will be assessed by comparing the parasitological clearance rate, determined by sustained parasitological clearance until 24 months of follow-up after treatment. Secondary assessments of PCR will be conducted at 1, 4, 6, 8, 12 and 18 months

As this is a double-blind study, this will not interfere with the schedule of events, since all participants will have all required samples planned at each visit. In addition, a qualitative and quantitative efficacy assessment will be performed, correlating incidence of and time to parasitological clearance with changes in *T. cruzi* serology.

The study manual of operations will provide full details regarding procedures for blood samples (tube types and number, aliquots volume), handling, storage, and shipment of the samples for laboratory evaluation. Quality assurance systems will be in place and described. Training of personnel in each of the activities described above will take place before initiation of this clinical trial. All parasitological and other

laboratory assessments will be performed blinded to treatment allocation. The PCR samples will all be evaluated by trained specialists in a central laboratory in each country, using harmonized protocols, and similar techniques. Quality control will be carried out in the two countries by the same team of molecular biology specialists.

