A control event rate is expected to be 10% of treatment failure (at least one positive PCR during follow up period) and a 20% of treatment withdrawn due to any AE. Control arm showing posterior probability of superiority of 97.5% or higher will be considered superior. This will be calculated for the experimental intervention versus the control group based on the observed data at the time of interim assessment with a superiority p-value stopping boundary of 0.010.

The decision for interim analysis will be made in a blinded manner (e.g., based on pooled number of events).

All analyses will be performed using Stata 13.0 for Windows.

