10.8 Efficacy Analysis

The primary efficacy endpoint is parasitological response, defined as sustained parasitological clearance at 24 months of follow-up after treatment, determined by serial qualitative PCR results. The primary analysis will be the comparison of the sustained parasitological clearance of each treatment arm. An efficacy interim analysis will be performed when participants complete 12 months from end of treatment. The stopping rule will be applied with no change planned on the sample size. At that point, if the condition of suspending the study is accomplished, participants will be considered as early treatment failures. Secondary efficacy analyses will further characterize differences in therapeutic response within this trial, namely:

- Parasite clearance at 6, 12 and 18 months.
- Serological response by conventional serology assessed at baseline and at 24 months of follow up after treatment.

For efficacy assessments, the EOT of each treatment arm will be defined according to the duration of the arm dosing regimen.

For PCR analyses, means and 95% confidence intervals will be presented per group and visit. In addition, time to sustained parasite clearance until 6, 12, 18 and 24 months of follow-up visits will be assessed using Kaplan– Meier survival analysis with log rank test for significance. Repeated measures analysis will also be performed. Multivariate analysis including those variables with a p-value<0.20 in the univariate model will be performed to define early and late predictors of a sustained parasitological response. The backwards method will be used to remove the variables that presented p-value greater than 0.05 in the multivariate analysis, until the obtention of the final model.

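### The supplementary Kaplan-Meier and log-rank analysis times sustained clearance, an event that falls mostly on one draw and cannot date treatment failure; time to first positive PCR would

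*Protocol*

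**What the plan says.** Protocol 10.3 and 10.8 carry the same sentence: "time to sustained parasite clearance until 6, 12, 18 and 24 months of follow-up visits will be assessed using" Kaplan-Meier analysis with a log-rank test. Protocol 3.1 describes the event in similar terms, planning an assessment "correlating incidence of and time to parasitological clearance with changes in" serology. No time to first positive PCR or time to relapse is defined.

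The sampling times are in section 7: "Blood samples for PCR will be collected at screening visit and at 1, 4, 6, 8, 12, 18 and 24 months after EOT". The schedule in section 12 agrees. No PCR is drawn during treatment or at the end-of-treatment visit.

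In giving the expected control rate for the interim analysis, 10.3 defines failure: "10% of treatment failure (at least one positive PCR during follow up period". The primary endpoint in 10.8 is "sustained parasitological clearance at 24 months of follow-up after treatment, determined by serial qualitative PCR results". Section 10.1 plans 224 per arm, with assumed failure of 10% on the standard regimen and 12% on a short regimen, a 15-point margin and a 10% allowance for losses.

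**The concern.** In a trial of treatment duration, a survival analysis is useful for showing whether and when parasitaemia returns. Sustained clearance is a poor event for that, for three reasons.

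- **Ties.** A participant who is negative throughout has the event at the first draw, so the curve is close to a single step there.
- **Dependence on later results.** A negative at month 1 becomes an event at month 1 only once the later results are known. Ordinary censoring assumes that event status at a given time can be read from what has been observed by then.
- **Conflict with the failure definition.** If the clearance clock may restart after a positive, a participant with one positive followed by negatives to month 24 has a clearance event here and is a failure under 10.3.

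At stake is the reading of a supplementary analysis. Its curves would say almost nothing about the timing of failure and could show a smaller difference between arms than the failure definition gives.

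**Working it through.** **1. The plan's sample size.** Inputs from 10.1: failure 10% and 12%, margin 15 points, one-sided 0.025, power 90%.
n = (1.960 + 1.282)² × (0.10×0.90 + 0.12×0.88) / (0.15 − 0.02)² = 10.51 × 0.1956 / 0.0169 = 121.6, so 122 per arm. With at least 60% PCR positive and 10% for losses: 122 / 0.6 × 1.1 = 223.7, so 224. The plan's figure is reproduced. The protocol gives no figure for the survival analysis itself.

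**2. Ties at the first draw.** Control: 224 × 10% = 22 failures, leaving 202 of 224 (90%) with the event at month 1. Short regimen: 224 × 12% = 27 failures, leaving 197 of 224 (88%). If none of the failures is transient, every event falls on that draw. If all are transient, 90% and 88% of events do.

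**3. Timing of failure.** Take 45 of 224 (20%) failing permanently in each arm, all first positive at month 1 in one arm and at month 18 in the other.

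| Event | Arm failing at month 1 | Arm failing at month 18 | Log-rank |
|---|---|---|---|
| Sustained clearance | 179 events at month 1, 45 censored at 24 | 179 events at month 1, 45 censored at 24 | chi-square 0, p = 1 |
| First positive PCR | 80% failure-free at month 12 | 100% failure-free at month 12 | p = 0.57 |

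The clearance curves are identical. The first-positive curves separate. With equal final totals that log-rank test is not significant either, so the gain here is in the curves.

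**4. Censoring.** Consider a participant negative at months 1, 4 and 6 and then lost. Scoring an event at month 1 assumes that the unseen results are negative. Censoring at month 6 keeps the participant at risk as not yet cleared, although any sustained clearance would already be dated month 1. Neither is valid. The 10% loss allowance corresponds to about 22 of 224 per arm.

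**5. Transient positives.** A participant negative at months 1, 4 and 6, positive at 8 and negative at 12, 18 and 24 is a failure under 10.3. If clearance may restart, the same participant clears at month 12. If half of failures were transient (assumed), 11 of 22 control and 14 of 27 short-regimen failures would be scored as cleared. Apparent clearance would be 213/224 = 95.1% and 211/224 = 94.2%, instead of 90.2% and 87.9%.

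**6. Effect on a margin-sized difference.** Assumptions, none of them in the protocol: failure 10% v 25%; 3% first positive at month 1 in both arms; other first positives spread evenly over the six later draws; each draw after a first positive again positive with probability q. Not cleared at month 24 means positive at that draw. For a later failure this has probability 1/6 + (5/6)q. The 3% cancels, so the apparent difference is 15 × (1/6 + 5q/6).

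| q | Apparent difference (points) |
|---|---|
| 0.3 | 6.25 |
| 0.6 | 10.0 |
| 0.9 | 13.75 |
| 1.0 | 15.0 |

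**7. Log-rank power.** At 10% v 25%, simulation under the assumptions of step 6 gives about 0.75 to 0.90 for sustained clearance against 0.85 to 0.90 for first positive at 122 per arm. At 224 per arm it gives 0.95 to 0.99 against 0.99. A separate model at 224 per arm, with 0, 25, 50 or 75% of failures transient, gives 0.99, 0.95, 0.93 and 0.91 against 0.99.

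**The case against.** The strongest reply is that this is a loosely worded supplementary analysis. It is introduced as an addition, it is absent from the endpoint table in section 3, and no decision rule uses it. Timing is covered elsewhere: the proportion positive at each visit is a named secondary endpoint, 10.8 lists clearance at 6, 12 and 18 months, and a repeated measures analysis is planned. The wording could be meant as duration of clearance, and an analysis plan could say so. If any positive rules out sustained clearance for good, the conflict with the failure definition disappears. All of this limits the point. It does not remove it: 3.1, 10.3 and 10.8 all name clearance as the event, and the ties and the censoring problem arise whether or not clearance may restart.

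Some stronger inferences are tempting and are not supported.

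- A reader might infer that the log-rank test has almost no power or carries almost no information. Power near 5% arises only if the event is the first negative PCR, and the protocol says sustained clearance. For that event the test behaves much like a comparison of final proportions (step 7).
- A reader might infer that the analysis favours the short regimens. The shrinkage in step 6 depends on an unknown share of transient positives and vanishes when positives persist. The log-rank result does not feed the non-inferiority conclusion.
- A reader might add that participants who are PCR negative at baseline have nothing to clear. That concerns the analysis population and would remain with any event.

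**Conclusion.** The point holds as a defect in the choice of event for one supplementary analysis. Three parts follow from the protocol's own event, draw times and rates: about 88 to 90% of participants have the event at a single draw, early losses cannot be validly censored, and the curves cannot date failure. The scoring of some failures as cleared is conditional: it needs the reading in which clearance may restart, and its size needs a rate of transient positives that the protocol does not give. Over the assumed range, a 15-point difference appears as about 6 to 15 points. Loss of log-rank power is modest, and nil if positives persist. The primary comparison of 24-month proportions is unaffected. The change is still worth making, because a better event is available from the same samples.

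**What to change.** In 10.3 and 10.8, replace the event with time from randomisation to first positive post-treatment PCR, censored at the last negative PCR, and define failure as in 10.3 (any positive during follow-up). Each failure is then dated at the draw where it is first seen, a participant lost early contributes time up to the last negative, and the event matches the failure definition. Align the phrase in 3.1. Two additions are optional and supportive: allowing for interval censoring between draws, and reporting the Kaplan-Meier difference in failure at 24 months with its 95% confidence interval. The cost is wording only; draws, visits and sample size stay as they are.
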